9.1.4 Telemetry

A 5-lead real-time telemetry ECG will be displayed for at least 4 hours on Day -1 while awake and again starting at -0.5 hours on Day 1 through at least 4 hours post initial-dose;

starting at 0.5 hours prior to the 3rd dose on Day 7 continuously through 4 hours post dose. (PI discretion based on ECG results) Any clinically relevant changes from baseline (Day 1, 4-hour recording) will be documented by a 12-lead ECG or an appropriate rhythm strip. These findings will be recorded in the subject's eCRF. Telemetry will be monitored by the PI, research nurse, or designee.

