7.3 Treatment Period

The specific order of evaluations conducted during the treatment period will be defined by the [REDACTED] Biometrics system.

7.3.1 Day 1

Prior to the administration of the first dose of study product, the following procedures will be performed:

- Brief physical examination focused on the examination of skin and oropharyngeal mucosa for evidence of bleeding and/or bruising (oral [gums] and evidence of hematoma, ecchymosis or petechia), brief neurological examination (mental status, motor system, and sensory system);
- Confirm that subject adhered to fasting requirements of at least 3 hours before the first dosing;
- Obtain vital signs (blood pressure, pulse rate, after being supine for 10 minutes, and orthostatic blood pressure and pulse rate (taken after 2 minutes in the standing position), respiratory rate and oral temperature;
- Obtain a triplicate 12-lead ECG;
- Obtain baseline blood sample for PK analysis ($t=0$), to be taken within 1 hour prior to first dose;
- Telemetry starting at -0.5 hours on Day 1 through at least 4 hours post the first dose;
- Randomization

All subjects will be administered the assigned study product or placebo. The total volume of each dose of the study product solution plus the rinse(s) and water will be 240 mL.

- The following procedures will be instituted to reduce incomplete or interrupted dosing of subjects:
In the event of partial dosing, either due to dosing error, or the subject coughing, gagging or spilling solution, the subject will only be followed for safety measurements as defined in [Section 5.3.3](#).

Following the administration of study product, the following procedures will be performed:

All physical exams, blood tests and ECGs after subjects have been dosed are obtained at approximately the same time each morning (within 2 hours).

- Obtain clinical chemistry, hematology, and coagulation;
- Obtain blood samples for PK analysis at 0.25 (± 5 min), 0.5 (± 5 min), 1 (± 10 min), 1.5 (± 10 min), 2 (± 10 min), 2.5 (± 15 min), 3 (± 15 min), 5 (± 30 min), 6 (± 30 min), 8 (± 30 min) hours (8 hour sample to be collected immediately before the second dose).
- Obtain vital signs (blood pressure and pulse rate including oral temperature and respiratory rate) at 1, 2, 3, 4, 5, 6 and 7 hours (± 15 minutes), after each administration of the study product. Vital signs should be taken after being supine for 10 minutes,

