
(a) Abbreviated physical examination (general appearance, heart, lungs, skin and abdomen) Day -1, Day 8 and Day 10, and brief neurological examination (mental status, motor system, and sensory system) will be done Day -1 through Day 8 and Day 10. In addition, brief physical examinations focused on the examination of skin and oropharyngeal mucosa for evidence of bleeding and/or bruising (oral [gums] and cutaneous) will be performed Days -1 through 8, and Day 10 (including a Day 1 examination prior to the first dose and 30 minutes after the 1st dose). Symptom directed/targeted physical examinations will be done at other study time points based on subject symptoms.
 
(b) Vital signs (blood pressure and pulse rate including oral temperature and respiratory rate) taken after 10 minutes supine rest; should be taken after ECG recordings (1 hour window for pre-dose procedures).
 
(c) At pre-dose, and hourly up until 2 hours after the third dose of the investigational product per day.
 
(d) Blood pressure and pulse rate taken after 2 minutes in standing position. At pre-dose, and hourly up until 2 hours after the third dose of the investigational product per day.
 
(e) Females only.
 
(f) Postmenopausal females only.
 
(g) A subset of hematology (PLT count), serum chemistry (AST, ALT), and coagulation (INR, PT, aPTT) assessments will be collected prior to the first dose only.
 
(h) Fecal occult assessments will be performed on Day 1 starting approximately 6 hours post first dose on every stool sample. On Day 15, fecal occult assessment may be performed as per discretion of the PI, and, if positive, followed until resolution.
 
(i) Triplicate 12-lead ECGs at baseline (Day 1 pre-dose); single 12-lead ECGs obtained at the same time each day for all residential days. [ECGs will be repeated for confirmation of any stopping criteria and at the PI's discretion].
 
(j) Telemetry for at least 4 hours on Day -1 and starting at -0.5 hours prior to the first dose (Day 1) and continuously through 4 hours post the first dose. Starting at 0.5 hours prior to the 3rd dose on Day 7 continuously through 4 hours post dose. (PI discretion based on ECG results)
 
(k) Pre-dose on Day 1
 
(l) Blood samples for PK analysis will be collected at pre-dose (0 hour) and after the first dose at 0.25 (±5 min), 0.5 (±5 min), 1 (±10 min), 1.5 (±10 min), 2 (±10 min), 2.5 (±15 min), 3 (±15 min), 5 (±30 min), 6 (±30 min), 8 (±30 min) hours (8 hour sample to be collected immediately before the second dose),
 
(m) One trough sample daily within fifteen (15) minutes before the first dose
 
(n) Immediately (within fifteen minutes) before the final dose, and at 0.25 (±5 min), 0.5 (±5 min), 1 (±10 min), 1.5 (±10 min), 2 (±10 min), 2.5 (±15 min), 3 (±15 min), 5 (±30min), 6 (±30 min), 8 (±30 min), 10 (±30 min), 12 (±30 min), and 14 (±30 min) hours after the final dose;
 
(o) One sample.
 
(p) Vomitus occult assessment will be done on all vomitus
												

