10. STATISTICAL METHODOLOGY

10.1 General

Data listings and summary statistics and statistical analyses will be performed for subjects included in the relevant analysis populations (All Subjects/ITT/Safety/PK).

For continuous data, summary statistics will include number of observations (n), the arithmetic mean, arithmetic standard deviation (SD), median, minimum (Min), and maximum (Max); for log-normal data (eg, the PK parameters: AUCs and C_{max}) the geometric mean and geometric coefficient of variation expressed as a percentage (CV%) will also be presented. For categorical data, frequency counts and percentages will be presented. For the calculation of summary statistics and statistical analysis, unrounded data will be used.

Baseline is defined as the last value for each assessment prior to the subject's first dose, including unscheduled values. Mean change from baseline is the mean of all individual subjects' change from baseline values. Each individual change from baseline will be calculated by subtracting the individual

subject's baseline value from the value at the timepoint. The individual subject's change from baseline values will be used to calculate the mean change from baseline using appropriate SAS[®] procedures such as Proc Univariate.

Missing values will not be imputed.

Data analysis will be performed using SAS[®] Version 9.3.

Analysis Data Model (ADaM) datasets will be prepared using Clinical Data Interchange Standards Consortium (CDISC) Analysis Data Model Version 2.1, and CDISC ADaM Implementation Guide Version 1.1. Pinnacle 21 Version 2.1.0 or higher will be utilized to ensure compliance with CDISC standards.

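### Protocol 9.1.4 takes as its telemetry baseline a Day 1 recording that is almost entirely post-dose; it should name a pre-dose recording (wrong as written, minor)

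*Protocol*

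**What the plan says.** Protocol 9.1.4 schedules telemetry on three days. It "will be displayed for at least 4 hours on Day -1 while awake and again starting at -0.5 hours on Day 1", and the Day 1 session continues to at least 4 h after the first dose. The third session runs from 0.5 h before to 4 h after the third dose on Day 7. The same section then sets the comparison rule: "Any clinically relevant changes from baseline (Day 1, 4-hour recording) will be documented by a 12-lead ECG" or a suitable rhythm strip. Findings documented in this way go into the eCRF.

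The Day 1 window is described consistently in three places:
- Section 9.1.4: "again starting at -0.5 hours on Day 1 through at least 4 hours post initial-dose".
- Section 7.3.1: "Telemetry starting at -0.5 hours on Day 1 through at least 4 hours post the first dose".
- Appendix IV, telemetry footnote: "starting at -0.5 hours prior to the first dose (Day 1) and continuously through 4 hours post the first dose".

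Other cardiac baselines are pre-dose. The ECG footnote in Appendix IV has "Triplicate 12-lead ECGs at baseline (Day 1 pre-dose); single 12-lead ECGs obtained at the same time each day for all residential days". Section 9.1.3 uses the Day 1 ECG as baseline for waveform and QTc, section 9.6 judges the QTcF change against the average of the pre-dose triplicate, and SAP 10.7.6 uses the mean of the Day 1 predose ECGs. The general rule in SAP 10.1 reads "Baseline is defined as the last value for each assessment prior to the" subject's first dose. SAP 10.7.7 says that telemetry will be listed.

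**The concern.** A baseline for a drug-safety comparison should be free of the drug. Here the named reference is the session that spans the first dose. Read literally, a rate, rhythm or conduction change in the first 4 hours after dosing lies inside the recording it is to be compared with. The Day 7 session, taken after six full days of dosing, is compared with a recording made mostly under drug. The one long drug-free session, on Day -1, is given no comparator role in 9.1.4.

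At stake is the bedside trigger for capturing a telemetry change by 12-lead ECG or rhythm strip. It has some weight because the post-dose procedures listed for Day 1 in section 7.3.1 include no 12-lead ECG. Telemetry, alongside hourly vital signs, is therefore the main listed cardiac recording in those hours. It is displayed in real time, and the documented findings are what enter the eCRF.

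**Working it through.** The documents state no percentage, so there is no figure of theirs to reproduce. The check is a share of recorded time.

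**Inputs**
- Pre-dose part of the Day 1 session: 0.5 h (9.1.4, 7.3.1, Appendix IV).
- Post-dose part: at least 4 h (9.1.4, 7.3.1), or through 4 h (Appendix IV).
- Day -1 session: at least 4 h while awake (9.1.4, 7.2.1). The Day -1 dose is a sham of masking solution, so no UV-4B has been given.

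**Formula:** post-dose share = post-dose hours / total hours in the reference recording.

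| Reading of the stated baseline | Calculation | Post-dose share |
|---|---|---|
| Whole Day 1 session at its minimum | 4 / (0.5 + 4) | 88.9% |
| Four hours in total, starting at -0.5 h | 3.5 / 4 | 87.5% |
| The 4 post-dose hours only | 4 / 4 | 100% |
| Session extended to 6 h post-dose | 6 / 6.5 | 92.3% |
| Session extended to 8 h post-dose | 8 / 8.5 | 94.1% |
| Day -1 recording | 0 / 4 | 0% |
| Day 1, -0.5 h to dosing | 0 / 0.5 | 0% |

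Every reading above that keeps the Day 1 session gives 87.5% or more. The minimum drug-free telemetry available is 4 + 0.5 = 4.5 h. The stated baseline uses at most 0.5 h of it, or 0.5 / 4.5 = 11.1%.

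**Is it a slip?** The reference is called a 4-hour recording. The session specified as (at least) 4 hours is Day -1; the Day 1 session is at least 4.5 h. Day -1 telemetry also sits under the heading Enrollment/Baseline (7.2). Both facts suggest that a minus sign is missing. The amendment log reproduces only the first sentence of 9.1.4, so it offers no second copy of the rule, and no other section restates it.

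**How far does it reach?**
- Adverse events: 9.2.1 treats what is present up to ingestion of the first dose as pre-existing, and 9.2.3 requires later conditions to be reported.
- Waveform change: 9.1.3 calls for repeat ECGs on a change from baseline tracings, and that baseline is the pre-dose Day 1 ECG.
- 12-lead ECGs on Days 2 to 8, 10 and 15: SAP 10.7.6 takes changes from the Day 1 predose mean.
- Halting on QTcF change: 9.6 uses the pre-dose triplicate average.
- Planned outputs: telemetry is listed only (SAP 10.7.7), with no change-from-baseline summary.

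**The case against.** The strongest reply is that this is a typing slip that experienced staff would read correctly. Telemetry is watched live by the investigator, a research nurse or a designee. The Day 1 trace begins before dosing, so a new rhythm after the dose would stand out against the preceding half hour and against Day -1. No averaging over the session is prescribed, so 89% is a share of clock time and not the size of a bias. The conflict with SAP 10.1 is one of definition only, since that rule serves subtraction of values and none is planned for telemetry.

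Most of this stands, and it limits the consequence. It does not rescue the wording. If the phrase is a slip, the controlling text still names the wrong session in a safety rule, and up to two sites apply it.

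A reader might go further and infer that first-dose cardiac effects need not be documented, or that an effect lasting from dose 1 to Day 7 would stay hidden. The documents do not support either reading. The sentence in 9.1.4 governs how a telemetry change is captured; adverse event reporting and the waveform-change rule apply regardless of it. A persisting effect that shows on a 12-lead ECG would meet repeated comparisons with the pre-dose triplicate. Nor does either document define a numeric telemetry endpoint whose Day 7 change could be driven towards zero.

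**Conclusion.** Wrong as written, minor severity. The stated telemetry baseline is about 88% to 100% post-dose on the readings that keep Day 1, and it is out of line with the pre-dose 12-lead baseline and the SAP's general rule. The conclusion rests on taking the printed Day 1 at face value and on the session windows being followed. If Day -1 was meant, the intended rule is sound and only the text needs correcting.

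The effect is confined to when a telemetry change is documented by ECG or rhythm strip in the Day 1 and Day 7 sessions. Subtler changes, where the judgement depends on the comparator, are the ones exposed. No endpoint, planned table or QTcF halting decision is affected.

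**What to change.** In Protocol 9.1.4, replace the parenthesis after the word baseline with a pre-dose definition: the Day -1 telemetry recording of at least 4 hours, supported by the Day 1 segment from -0.5 h to dosing. The post-dose share of the reference then falls from about 89% to 0%, and both the Day 1 post-dose and Day 7 sessions are compared with a drug-free recording.

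The cost is one phrase in the next amendment. The Day -1 recording is already scheduled for every subject, and monitoring times and clinical action do not change. The SAP needs no edit: the new wording agrees with its pre-dose rule, and telemetry remains a listing.

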9.1.5 Physical Examination

A complete physical examination, including examination of the skin, head, eyes, ears, nose, and throat; lymph nodes, heart; lungs; abdomen; extremities; and joints will be performed at screening and Day 15 (± 1) the follow-up visit. Breast, genital, and rectal examinations will not be performed. The complete physical examination at screening will also include height, weight and calculation of the BMI.

An abbreviated physical examination (general appearance, heart, lungs, skin, and abdomen) and abbreviated neurological examination (mental status, motor system, and sensory system) will be done (Day -1 through 8), and on Day 10 (± 1).

Brief physical examinations focused on examination of skin and oropharyngeal mucosa for evidence of bleeding and/or bruising (oral [gums] and cutaneous) will be performed on each day while admitted to the clinic (Day -1 through 8) and on Day 10 (± 1).

Targeted physical examinations will be done at other study time points if an AE is reported or if the PI or designee feels that it is in the best interest of the study subject.

9.1.6 Clinical Laboratory Testing

Laboratory testing will be utilized to evaluate safety on an ongoing basis through the treatment and follow-up periods according to [Section 8.2](#). Laboratory reports from the local clinical laboratory will be provided to the clinic on the same day as sample collection and will be filed in the subjects' charts. Any values outside of the laboratory defined range will be flagged as such by the clinical laboratory.

9.1.7 Evaluation of Hypersensitivity Reactions

Examples of hypersensitivity (HS) reactions include erythema of oropharyngeal and conjunctival membranes, rhinitis, coryza, breathing difficulties including wheezing, dyspnea and stridor, and dermatologic findings to include diffuse pruritus, macular rashes and or vesiculation. Laboratory abnormalities suggestive of HS reaction (e.g., peripheral eosinophilia) require clinical corroboration.

Any evidence of HS reaction during study requires cessation of dosing pending physician evaluation and clinical corroboration. If HS reaction follows dosing, AE or SAE will be

recorded in accordance with physical monitoring criteria or laboratory abnormalities noted in [Appendix II](#).

The Phase 1 treatment facility is capable of managing all types of HS reactions from HS type I-IV (e.g., with bedside epinephrine, diphenhydramine, terbutaline and albuterol nebulizers and oral and/or systemic steroids). [REDACTED] will follow their Standard Operating Procedures (SOPs) for treatment of HS reactions. Please see general anaphylaxis protocol ([Appendix V](#)).

9.2 Methods and Timing for Assessing, Recording, and Analyzing Safety Parameters

9.2.1 Adverse Events

ICH E6 defines an AE as any untoward medical occurrence in a patient or clinical investigation subject administered a pharmaceutical product regardless of its causal relationship to the study treatment. An AE can therefore be any unfavorable and unintended sign (including an abnormal laboratory finding), symptom, or disease temporally associated with the use of a medicinal (investigational) product. The occurrence of an AE may come to the attention of study personnel during study visits and interviews of a study recipient presenting for medical care, or upon review by a study monitor.

All AEs including local and systemic reactions not meeting the criteria for “SAEs” should be captured on the appropriate eCRF. Information to be collected includes event description, time of onset, clinician’s assessment of severity, relationship to study product (assessed only by those with the training and authority to make a diagnosis, which would include Medical Doctor, Physician’s Assistant, Nurse Practitioner, Doctor of Osteopathy, or Dentist), and time of resolution/stabilization of the event. All AEs occurring while in study must be documented appropriately regardless of relationship. All AEs will be followed to adequate resolution as determined by the PI.

Any medical or laboratory condition that is present at the time that the subject is screened up through ingestion of the first dose should be considered as baseline/pre-existing condition and not reported as an AE. However, if it deteriorates at any time during the study after ingestion of the first dose, it should be recorded as an AE.

All AEs must be assessed for severity and relationship to study product. The PI will make an assessment of severity for each AE and SAE reported during the study and will assign it to one of the following categories:

Mild: An event that is easily tolerated by the subject, causing minimal discomfort and not interfering with everyday activities;

Moderate: An event that is sufficiently discomforting to interfere with normal everyday activities;

Severe: An event that prevents normal everyday activities

In addition, all AEs will be graded (Grade 1 to 4) according to the FDA Guidance for Industry: *Toxicity Grading Scale for Healthy Adult and Adolescent Volunteers Enrolled in Preventive Vaccine Clinical Trials September 2007* and the *Division of Microbiology and Infectious Diseases (DMID) Adult Toxicity Table November 2007* as modified for this study ([Appendix II](#)). For clinical or laboratory observations not addressed by the toxicity grading criteria, Grade 0=absent will be used in the AE CRF to indicate the toxicity grading criteria do not apply.

Relationship to Study Products: The PI's assessment of an AE's relationship to the study product is part of the documentation process, but it is not a factor in determining what is or is not reported in the study. If there is any doubt as to whether a clinical observation is an AE, the event will be reported. All AEs must have their relationship to study product assessed using the terms: related or not related. In a clinical trial, the study product must always be suspect. To help assess, the following guidelines will be used.

Related – There is a reasonable possibility that the study product caused the AE. Reasonable possibility means that there is evidence to suggest a causal relationship between the study product and the AE. If an alternate etiology is not identified, the AE must be considered related to study product.

Not Related – There is not a reasonable possibility that the administration of the study product caused the event.

AE's should be documented from time of dose administration through the final study visit.

9.2.2 Serious Adverse Events

Serious Adverse Event: An AE or suspected adverse reaction is considered “serious” if, in the view of either the PI or Sponsor, it results in any of the following outcomes:

- Death;
- Is life-threatening: an AE is considered “life-threatening” if, in the view of either the PI or Sponsor, its occurrence places the patient or subject at immediate risk of death. It does not include an AE, had it occurred in a more severe form, might have caused death;
- Requires hospitalization or prolongation of existing hospitalization;
- Results in disability/incapacity;
- Is a congenital anomaly or birth defect; or
- Is considered an important medical event when the event does not fit the other outcomes, but the event may jeopardize the patient and may require medical or surgical intervention (treatment) to prevent one of the other outcomes. Examples include

allergic bronchospasm (a serious problem with breathing) requiring treatment in an emergency room, serious blood dyscrasias (blood disorders) or seizures/convulsions that do not result in hospitalization. The development of drug dependence or drug abuse would also be examples of important medical events.

All SAEs will be:

- Recorded on the appropriate eCRF;
- Followed through to resolution by a study PI;
- Reviewed and evaluated by a study PI.
- Recorded on the SAE Data Form and forwarded within 24 hours by fax or email to Emergent Pharmacovigilance.
- Sent to DMID Medical Monitor

Dosing will be paused for any SAE until causality is fully assessed by the PI and SMC. Dosing will cease if the SAE is determined to be either drug-related or unknown, and may resume if the SAE is determined to be not drug-related by the PI and SMC.

SAE's should be documented from time of dose administration through the final study visit.

9.2.3 Procedures to be followed in the Event of Abnormal Laboratory Test Values or Abnormal Clinical Findings

The collection of laboratory data is listed in [Section 8.2.1](#). The normal reference ranges utilized in this study are shown in the current version of the Laboratory Protocol Reference Ranges published by Lab. The grading of abnormal clinical findings are based on the FDA Guidance for Industry: *Toxicity Grading Scale for Healthy Adult and Adolescent Volunteers Enrolled in Preventive Vaccine Clinical Trials September 2007* and *Division Of Microbiology And Infectious Diseases (DMID) Adult Toxicity Table November 2007* as modified for this study (see [Appendix II](#)).

Any medical condition or graded laboratory value (according to [Appendix II](#)) after ingestion of the first dose or deterioration from the baseline condition will be reported and followed as an AE or, as appropriate, SAE. Attempts will be made to follow the subject closely to determine the outcome and duration of an event. Additional assessments including the repeat of laboratory tests and ECGs will be performed in an effort to monitor the subject as appropriate. If an event is ongoing at the time of study termination, permission will be requested from the subject to continue follow-up until the site PI or designee deems the event to be resolved, chronic, or the subject's condition to be medically stable. Abnormal ECGs, at the discretion of the PI, will be reviewed by a cardiologist.

